6.4.1.3 Subgroup Analysis for Primary Efficacy Endpoint

The co-primary efficacy endpoint analyses will be repeated for the following subgroups using the simplified MMRM model. However, p-values for treatment difference will not be provided. Descriptive statistics and least square mean (SE) will be provided for each subgroup.

The subgroups will be defined below.

- Smoking status (current versus former/never), per randomization strata.
- Race (African-American vs Non-African-American, Asian vs Non-Asian, White vs Non-White)
- BMI (>=18.5 kg/m² to <25 kg/m², >=25 kg/m² to <30 kg/m², >=30 kg/m²)
- Age (<55, >=55)

For subjects who are recorded more than one race, the subjects will be excluded from the race subgroups, except:

- If no African-American is recorded, then the subject is included in Non-African-American subgroup
- If no Asian is recorded, then the subject is included in Non-Asian subgroup
- If no White is recorded, then the subject is included in Non-White subgroup.

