1.3.2 Summary of Clinical Studies

To date, 10 clinical studies have been completed with fezolinetant; 6 phase 1 studies (ESN364-CPK-101, ESN364-CPK-102, ESN364-CPK-103, 2693-CL-0020, 2693-CL-0006 and 2693-CL-0009) and 4 phase 2 studies (ESN364_HF_204, ESN364-UF-02, ESN364-PCO-201 and ESN364_HF_205). Two of the 4 phase 2 studies were performed in women with MR-VMS (Studies ESN364_HF_204 and ESN364_HF_205). The 10 completed studies with fezolinetant are shown in Table 2.

The pharmacokinetics of fezolinetant were characterized in studies in healthy subjects and in patients with VMS. After orally intake, fezolinetant showed generally dose proportional pharmacokinetics at doses between 20 and 60 mg once daily in female subjects. Peak concentration (C_{max}) was generally reached within 1 to 4 hours postdose with terminal half-life ($t_{1/2}$) ranging between 4 to 6 hours in healthy subjects and patients. With a once daily dose regimen, steady state in plasma concentrations are approximately achieved by day 2 with minimal accumulation. Low plasma protein binding of fezolinetant (50%) was observed with almost equal distribution of fezolinetant into red blood cells and plasma, with a blood-to-plasma ratio of 0.9.

Fezolinetant undergoes extensive metabolism, primarily by CYP1A2 enzyme, to form the major metabolite ES259564. A strong CYP1A2 inhibitor (fluvoxamine) increased fezolinetant AUC and C_{max} approximately 9-fold and 1.8-fold, respectively, while smoking can decrease AUC and C_{max} to a geometric LS mean ratio of 48.29% and 71.74%, respectively (study 2693-CL-0006).

In a recently completed mass balance study (ESN364_CPK_103), the routes of excretion of fezolinetant were via urine (76.9%) and feces (14.7%). In urine, a mean of 1.1% of the administered fezolinetant dose was excreted unchanged and 61.7% of the administered dose was excreted as metabolite ES259564.

Fezolinetant did not show clinically significant food effects on its pharmacokinetic exposure parameters (study ESN364_CPK_101). Based on population pharmacokinetic modeling analyses, body weight was not identified as an important predictor of AUC. However, male subjects are predicted to have 53.2% reduction AUC and 14.9% reduction in C_{max} , comparing to females. Asian population was predicted to have a 25% increase in steady-state C_{max} and AUC, which is consistent with clinical observations (study 2693-CL-0020).

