3.2 Inclusion Criteria

Subject who meets all of the following criteria will be eligible to participate in the study:

1. Institutional Review Board (IRB)/Independent Ethics Committee (IEC)-approved written informed consent and privacy language as per national regulations must be obtained from the subject or legally authorized representative prior to any study-related procedures
2. Subject is born female, aged ≥ 40 years and ≤ 65 years of age at the screening visit.
3. Subject has a body mass index ≥ 18 kg/m² and ≤ 38 kg/m².
4. Subject must be seeking treatment or relief for VMS associated with menopause and confirmed as menopausal per 1 of the following criteria at the screening visit:
 - Spontaneous amenorrhea for ≥ 12 consecutive months
 - Spontaneous amenorrhea for ≥ 6 months with biochemical criteria of menopause (FSH > 40 IU/L); or
 - Having had bilateral oophorectomy ≥ 6 weeks prior to the screening visit.
5. Within the 10 days prior to randomization, subject must have a minimum average of 7 to 8 moderate to severe HFs (VMS) per day, or 50 to 60 per week.
6. Subject is in good general health as determined on the basis of medical history and general physical examination, including a bimanual clinical pelvic examination and clinical breast examination devoid of relevant clinical findings, performed at the screening visit; hematology and biochemistry parameters, pulse rate and/or blood pressure and ECG within the reference range for the population studied, or showing no clinically relevant deviations, as judged by the investigator.
7. Subject has documentation of a normal/negative or no clinically significant findings mammogram (obtained at screening or within the prior 12 months of study enrollment). Appropriate documentation includes a written report or an electronic report indicating normal/negative or no clinically significant mammographic findings.
8. Subject is willing to undergo a TVU to evaluate the uterus and ovaries at screening and at week 52 (EOT), and for subjects who are withdrawn from the study prior to completion, a TVU at the ED visit.
9. Subject is willing to undergo an endometrial biopsy at screening and at week 52 (EOT), for subjects with uterine bleeding, and for subjects who are withdrawn from the study prior to completion. The endometrial biopsy obtained at screening must be considered evaluable.

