6.4.1.2 Sensitivity Analysis for Primary Efficacy Endpoints

The following sensitivity analyses will be performed for the primary efficacy endpoints to assess the robustness of the primary analysis.

MMRM model based on PPS populations

Supportive analyses will be carried out for the co-primary efficacy endpoints based on the PPS populations. The data will be analyzed using the same MMRM model as the primary analyses, but the comparison of interest is a particular week within each population (Week 4 when using PPS4, and Week 12 when using PPS12).

Simplified MMRM model

The analysis for each of the co-primary endpoints also will be conducted using a simplified MMRM model with treatment group and week as factors, with baseline measurement as a covariate as well as an interaction of treatment by week and baseline by week.

Discontinuation-reason based multiple imputation

The MMRM analysis that will be used to perform the primary analysis of the primary endpoint assumes that missingness is at random. That is, the model assumes that the trajectory of VMS events over time for subjects who prematurely discontinue is similar to the trajectory for those observed in their own treatment arm which is valid so long as that assumption is reasonable.

Discontinuation-reason based multiple imputation (MI) will be used to examine the sensitivity of the primary analysis results to departures from that underlying assumption and will assess a situation where data for subjects who discontinue early follow a pattern which is missing not at random. Specifically, MI will be used for imputation of missing data, using "Jump to Reference" algorithm (where placebo is the reference group) [Carpenter et al. 2013] for subjects who discontinue active treatment due to AEs (AE reported as primary study drug treatment status in the End of Treatment eCRF). The analysis will be implemented using the general three-step process (imputation phase, followed by analysis phase, followed by pooling phase) described in O'Kelly and Ratitch, 2014.

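### The lowest BMI subgroup starts at 18.5 kg/m² although eligibility starts at 18, and the subgroup section names no treatment difference, interval or smoking contrast

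*SAP*

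**What the plan says.** **BMI.** Inclusion criterion 3 (Protocol 3.2, repeated in the synopsis) is "Subject has a body mass index ≥ 18 kg/m² and ≤ 38 kg/m²". Protocol 7.4.1.3 lists BMI as a subgroup factor without cut-points. The 12-week SAP, section 6.4.1.3, supplies three categories: ">=18.5 kg/m² to <25 kg/m²", then 25 to below 30, then 30 and above.

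**Subgroup model and output.** Section 6.4.1.3 repeats the co-primary analyses in each subgroup with the simplified model of section 6.4.1.2, described as a "simplified MMRM model with treatment group and week as factors, with baseline measurement as a covariate" plus treatment-by-week and baseline-by-week terms. On output it says two things: "However, p-values for treatment difference will not be provided" and "Descriptive statistics and least square mean (SE) will be provided for each subgroup".

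**Smoking.** One listed subgroup is "Smoking status (current versus former/never), per randomization strata". Randomization is stratified on the same factor (12-week SAP 2.3), and the primary MMRM (6.4.1.1) carries smoking as a main effect only. Protocol 1.3.2 reports that smoking can lower AUC and Cmax "to a geometric LS mean ratio of 48.29% and 71.74%, respectively".

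**The concern.** Two separate things are at issue.

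First, BMI categories should cover the eligible range. These do not, and the section has no rule for a woman below 18.5. Tables built to the SAP would drop her from every BMI row, and the BMI rows would no longer account for all women in the FAS.

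Second, smoking is a subgroup with a documented reason to look: the sponsor's own pharmacokinetic data show lower exposure, and the trial stratifies for it. The useful quantities are the drug-placebo difference in each stratum, its uncertainty, and how far the two differences diverge. The section names none of them. Separate LS means for smokers and non-smokers, shown without an interval on the difference, make it easy to over-read a chance gap.

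**Working it through.** **1. BMI coverage.**

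| Source | Range (kg/m²) |
|---|---|
| Eligible (Protocol 3.2) | 18 to 38, both ends included |
| Subgroups (SAP 6.4.1.3) | 18.5 to <25; 25 to <30; ≥30 |
| Eligible but unassigned | 18.0 to <18.5 |

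The uncovered band is 18.5 − 18.0 = 0.5 kg/m² wide. The documents give no BMI distribution, so the number of women in it is unknown. If 0% to 1% of 450 women are affected (an assumption), that is 0 to about 4 women.

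**2. What the 12-week SAP names as output, side by side.**

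- 6.4.1.1, primary analysis: LS mean contrasts with 95% CI and p-values.
- 6.4.1.2, multiple imputation: difference in LS means, its SE and 90% CI at Weeks 4 and 12.
- 6.4.4, anchor-based responders: odds ratio with 95% CI.
- 6.4.1.3, subgroups: descriptive statistics and LS mean (SE); no difference, CI or between-stratum contrast is named.

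**3. Precision to expect for smoking (frequency endpoint).**

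Inputs from the documents: SD 5, difference 2.0, 2-sided alpha 0.025, 120 per arm, and 150 per arm after allowing 20% dropout (12-week SAP section 3). The smoker share is not given; 10% to 30% is assumed.

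*Plan's own figure.* For 120 per arm, a difference of 2.0 and SD 5, the normal approximation gives 80.4% power and the exact noncentral t gives 80.0%, against 79% stated. The planning inputs reproduce to within about one point.

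*Formulas.* SE of the difference in smokers = 5 × √(2/n_s), with n_s smokers per arm. SE in non-smokers = 5 × √(2/n_n). SE of the contrast between strata = √(SE_s² + SE_n²). The 95% half-width is 1.96 × SE.

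| Per arm | Smoker share | n_s | SE in smokers | Half-width, smokers | SE of contrast | Half-width, contrast |
|---|---|---|---|---|---|---|
| 120 | 10% | 12 | 2.04 | 4.0 | 2.15 | 4.2 |
| 120 | 20% | 24 | 1.44 | 2.8 | 1.61 | 3.2 |
| 150 | 20% | 30 | 1.29 | 2.5 | 1.44 | 2.8 |
| 150 | 30% | 45 | 1.05 | 2.1 | 1.26 | 2.5 |

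Worked example, first row: 5 × √(2/12) = 2.04. With 108 non-smokers per arm, 5 × √(2/108) = 0.68. √(2.04² + 0.68²) = 2.15, and 1.96 × 2.15 = 4.2.

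For severity (SD 1, planned difference 0.40), the corresponding ranges are 0.41 to 0.80 in smokers and 0.49 to 0.84 for the contrast.

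*Would a test help?* With power = Φ(D/SE − 1.96) + Φ(−D/SE − 1.96), a 2-sided 5% interaction test for frequency has 7.5% to 12.5% power if the effect is 1.0 per day smaller in smokers, and 15.3% to 35.5% if it is 2.0 smaller. These two sizes are illustrative. The sensible product is therefore an estimate with an interval.

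**The case against.** **On BMI:** the affected women may number none, they remain in the primary analysis, and nothing requires subgroups to add up to the FAS; section 6.4.1.3 itself leaves some women with more than one recorded race out of race subgroups. All of this stands and limits the size of the point. It does not remove the mismatch: the race omission is a stated rule, whereas nothing is said about BMI below 18.5. The SAP's demographic age groups (6.2.3), by contrast, extend even to ineligible ages.

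**On smoking:** a reader might infer that the planned output cannot show whether the effect differs in smokers. The documents do not support that. Smoking is a named subgroup and efficacy output is by treatment group (6.4), so LS mean (SE) by arm in two disjoint strata lets a reader form each difference, an approximate interval and the contrast. It can also be argued that repeating the co-primary analyses carries their LS mean contrasts and 95% CIs along, since only p-values are expressly withheld, and that table layouts sit in separate specifications not available here. That is fair; the text leaves the matter open.

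A reader might also infer that smoking is the only modifier with a pharmacokinetic rationale. Protocol 1.3.2 contradicts this: it predicts 25% higher steady-state Cmax and AUC in the Asian population, and an Asian subgroup is planned.

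Nor does lower exposure imply a proportionally smaller effect. AUC falls by 100 − 48.29 = 51.7%, but Cmax by only 100 − 71.74 = 28.3%. The sponsor's model (Protocol 2.2.2) moves only from −2.11 to −2.37 between 30 mg and 45 mg.

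Finally, leaving out p-values is not a defect. Separate subgroup p-values would not test whether effects differ, and precision is too low for a useful test.

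**Conclusion.** The BMI category is wrong as written: eligible women with a BMI of 18.0 to below 18.5 have no subgroup. The consequence is very small, probably a handful of women at most, and no inference from the primary analysis changes.

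The smoking part is a reporting gap, not an error. Section 6.4.1.3 does not name the drug-placebo difference, its CI or a contrast between smoking strata, although other sections of the same SAP name differences with intervals and there is a stated reason to look at smokers. Adding them is a cheap improvement. What they would show is limited: under the assumed 10% to 30% smokers, the half-width in smokers (2.1 to 4.0 VMS per day) is at least as large as the planned effect of 2.0.

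These widths rest on the assumed smoker share, SD 5, 120 to 150 women per arm and a two-sample formula without baseline adjustment, so they are illustrative. Both parts are minor.

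**What to change.** 1. In 12-week SAP 6.4.1.3, relabel the lowest BMI category as <25 kg/m². It then covers every eligible woman, and also anyone enrolled in error below 18. Cost: one label.
2. State that each subgroup table shows the LS mean difference from placebo for each dose with a 95% CI, alongside the LS mean (SE) already planned. Cost: extra columns.
3. For smoking, add an exploratory contrast of the treatment effect between strata, with 95% CI, for each dose and co-primary endpoint at Weeks 4 and 12. It can come from one MMRM with treatment-by-smoking-by-week terms. Give no p-value and no alpha.

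The primary analysis and the data collected do not change. The downside is wide intervals that need cautious wording: a lack of visible difference must not be read as evidence of equal effect, nor a visible gap as evidence of modification. If the SAP is already final, its section 1 gives the route: document and justify the change in the clinical study report.

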6.4.2 Analysis of Key Secondary Efficacy Endpoint

The PROMIS SD SF 8b scale will be analyzed using MMRM, similar to the primary analysis of the co-primary endpoints, with spatial power as the backup covariance structure.

If all the co-primary endpoints are statistically significant between fezolinetant and placebo at both doses, then the 5% alpha from the analysis of the co-primary endpoints will be passed to the key secondary endpoint as part of the family-wise error rate.

As a sensitivity analysis, the analysis will be repeated by excluding data that are impacted by COVID-19, which includes the data recorded after the subjects were diagnosed of COVID-19, after study drug discontinuation due to COVID-19, during dose interruption due to COVID-19, and visits that are out of protocol window due to COVID-19 recorded in the eCRF.

6.4.3 Analysis of Secondary Efficacy Endpoints

The mean change in the frequency and severity of moderate and severe VMS from baseline to each week up to week 12 comes from the same model as the co-primary analyses, but examines the results at all weeks.

For percent reduction at weeks 4 and 12, an MMRM model as described in Section 6.4.1.1 will be used.

For each of the secondary responder endpoints, logistic regression will be used for the analysis for each week and endpoint. The analyses will include the treatment group and smoking status (current vs. former/never) as factors and baseline measurement (mean frequency of vasomotor symptoms) as a covariate.

For these responder endpoints, the number of subjects who achieve the reduction will be summarized by study week with descriptive statistics for each treatment arm. A Kaplan-Meier estimate will be used to estimate the time to response. Smooth average (SA) will be used for the time to response. SA value for day X-1, day X and Day X+1 would be assigned to day X. The time to response will be the first day with at least 50% (or 100%, or the exploratory endpoints 75%, 90%) response for both original numbers and SA number. For the non-responders, it will be censored at the end of the last day of the double-blind treatment (e.g., 8am the following day).

Comparisons between the fezolinetant and placebo will be calculated based on the odds ratio using a 2-tailed 95% confidence interval (CI) and p-values.

PGI-C VMS score will be analyzed using Cochran Mantel Haenszel (CMH) test with modified ridit scores.

For the changes in the frequency and severity of moderate and severe VMS from baseline to each week up to week 12 that are derived from diary data, the analysis will be repeated by excluding diary data that are impacted by COVID-19, which includes the diary data recorded after the subjects were diagnosed of COVID-19, after study drug discontinuation due to COVID-19, and during dose interruption due to COVID-19.

For the PGI-C VMS scores that are collected by visit, the analysis will be repeated by excluding data that are impacted by COVID-19, which includes the data recorded after the subjects were diagnosed of COVID-19, after study drug discontinuation due to COVID-19, during dose interruption due to COVID-19, and visits that are out of protocol window due to COVID-19 recorded in the eCRF.

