4.5 Assignment and Allocation

Subjects will be randomized in a 1:1:1 ratio to a treatment arm according to the randomization schedules and stratified by smoking status (active smoker or non-smoker) through IRT. Subjects who complete the 12-week treatment period and received placebo will be randomized to either fezolinetant 30 mg or 45 mg. The extension period will remain blinded to the site personnel and participating subjects. The site personnel will dispense the treatment according to the IRT system's assignment. Specific procedures for randomization through the IRT are contained in the study procedures manual.

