7.4.2.2 Secondary Endpoints

For percent reduction at weeks 4 and 12, an MMRM model as described in [Section 7.4.1.1 Co-Primary Analysis] will be used. Additional calculations of severity will be described in the SAP and will also be analyzed as described in Section 7.4.1.1 Co-Primary Analysis.

For each of the secondary responder endpoints, logistic regression will be used for the analysis for each week and endpoint. A missing value will be imputed as a nonresponder.

PGI-C will be analyzed using Cochran Mantel Haenszel test.

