7.4.3 Analysis of Exploratory Endpoints

Percent reduction, PROMIS (SD and SRI total scores), MENQOL total, EQ-5D domain scores and WPAI-VMS total score will be assessed using an MMRM model as described in [Section 7.4.1.1 Co-Primary Analysis]. Percent reduction and absolute reduction will be analyzed as described for the secondary responder endpoints. PGI-S will be analyzed using Cochran Mantel Haenszel test adjusted for baseline score. The median change in serum concentrations of sex hormones and sex hormone-binding globulin (SHBG) from baseline to weeks 4 and 12 and the mean change in serum concentrations of BSAP, P1NP and CTX from baseline to week 12 will be summarized.

NOTE: Assessments after the 12-week placebo-controlled period are descriptive only, because there is no placebo control.

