2.3 Randomization

The first 12 weeks of the study are double blind. Subjects will be randomized to receive fezolinetant or placebo in a blinded fashion such that neither the investigator, sponsor's study management team, clinical staff, nor the subject will know which agent is being administered. The randomization number will be assigned based on information obtained from the Interactive Response Technology (IRT).

Subjects will be randomized in a 1:1:1 ratio to a treatment arm according to the randomization schedules and stratified by smoking status (current smoker vs former/never) through IRT. Subjects who complete the 12-week treatment period and have received placebo will be randomized to either fezolinetant 30 mg or 45 mg for the extension period. The assigned treatment in the extension period will remain blinded to the site personnel and participating subjects. The site personnel will dispense the treatment according to the IRT system's assignment. Specific procedures for randomization through the IRT are contained in the IRT specifications manual.

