6.4.4 Analysis of Exploratory Endpoints

Assessment of the mean change in the frequency and severity of mild, moderate and severe VMS from baseline to each week up to week 12 will be analyzed using the same MMRM model as the primary analyses.

For non-VMS efficacy endpoints Visits are used rather than weeks, as described in Section 6.10.1.1.

Percent reduction, PROMIS (SD and SRI total scores), MENQOL (domain and total scores), and WPAI-VMS domain scores will be assessed using an MMRM model as described in [Section 6.4.1.1 Co-Primary Analysis].

VMS responders will be analyzed as described for the secondary responder endpoints.

PGI-S and PGI-C (SD) and EQ-5D domain scores-will be summarized and analyzed using Cochran Mantel Haenszel (CMH) test with modified ridit scores. PGI-S and EQ-5D will also be adjusted for the baseline score. The mean and standard deviation will also be provided for the EQ-5D domain scores.

The severity calculation excludes mild events at both baseline and post-baseline, using the same model as the primary analyses.

The mean change in the severity of moderate and severe VMS from baseline to each week up to week 12 (both baseline and post-baseline severity include only moderate and severe VMS events in the calculation) will be analyzed using the same MMRM model as the primary analyses.

The median change in serum concentrations of sex hormones and sex hormone-binding globulin (SHBG) from baseline to weeks 4 and 12 will be summarized.

The daily frequency of moderate and severe VMS for the first week will be summarized and graphically displayed by each day.

An exploratory analysis will be conducted using the thresholds for clinical meaningful within subject change from an anchor based analysis.

In order to provide further context for interpretation of change in the frequency of hot flashes, the anchor based analysis will be conducted to empirically define the threshold for meaningful within-subject reduction. A separate Psychometric Analysis Plan (PAP) [RTI Health Solutions] will provide the detailed description of the psychometric analytic methods to be used in determining the clinically meaningful within-subject reductions at week 4 and week 12. The thresholds will be estimated according to the prespecified PAP.

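### The CMH tests for PGI-C VMS and PGI-C SD name no stratum, although smoking status is the only factor that randomization is stratified by

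*SAP*

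**What the plan says.** Randomization is 1:1:1. The 12-week SAP (2.3) describes it as "stratified by smoking status (current smoker vs former/never) through IRT", and the protocol (4.5) as "stratified by smoking status (active smoker or non-smoker) through IRT". No other stratification factor is listed.

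Smoking status is a factor in the co-primary MMRM (protocol 7.4.1.1; 12-week SAP 6.4.1.1), in the secondary responder logistic models (6.4.3) and in the logistic model for threshold-based response (6.4.4).

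The rank tests are written differently:

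- **PGI-C VMS (secondary).** Protocol 7.4.2.2: "PGI-C will be analyzed using Cochran Mantel Haenszel test". 12-week SAP 6.4.3: "PGI-C VMS score will be analyzed using Cochran Mantel Haenszel (CMH) test with modified ridit scores". Neither names a stratum.
- **PGI-C SD, PGI-S SD and EQ-5D domain scores (exploratory).** 12-week SAP 6.4.4: these are "analyzed using Cochran Mantel Haenszel (CMH) test with modified ridit scores. PGI-S and EQ-5D will also be adjusted for the baseline score". Protocol 7.4.3: "PGI-S will be analyzed using Cochran Mantel Haenszel test adjusted for baseline score". PGI-C SD has no stratum. PGI-S SD and EQ-5D have baseline score, and smoking is not mentioned.

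No section says that the PGI-C tests are unstratified, and none gives a reason for leaving smoking out. The 52-week SAP is descriptive only (6.1), so the point concerns the 12-week SAP alone.

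**The concern.** When randomization is balanced within strata, the treatment contrast is already free of between-stratum variation. An unstratified test still counts that variation in its variance estimate, so it is somewhat conservative whenever the stratification factor predicts the outcome. The usual practice is to carry the factor into the analysis, as this SAP does in its MMRM and logistic models.

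Reproducibility is also at stake. Modified ridit scores are computed within strata, so a stratified and an unstratified run on the same data can give different p-values. The section does not tell the programmer which one is meant.

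The stake is limited to the precision and clarity of one secondary and one exploratory test.

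**Working it through.** **1. The plan's own figures.** The documents give no power or precision figure for any CMH test. The nearest is the sample-size calculation (12-week SAP section 3): 120 evaluable per arm, two-sided alpha 2.5%, SD 5. For a difference of 2.0 the noncentrality is 2.0 / (5 × √(2/120)) = 3.10. Power for differences of 2.0, 2.3 and 2.5 is 80.0%, 90.4% and 94.6% by the exact noncentral t, against 79%, 90% and 94% stated. The dropout inflation is 120 / (1 − 0.20) = 150, as stated. These figures reproduce, and 120 per arm is used below.

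**2. Share of variance that stratifying removes.** Let p be the share of current smokers and d the smoker/non-smoker difference in PGI-C in within-stratum SDs. Both are assumptions. Then R² = p(1−p)d² / (1 + p(1−p)d²).

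- p = 0.10, d = 0.25: 0.005625 / 1.005625 = 0.56%
- p = 0.25, d = 0.25: 0.01172 / 1.01172 = 1.2%
- p = 0.10, d = 0.5: 0.0225 / 1.0225 = 2.2%
- p = 0.25, d = 0.5: 0.046875 / 1.046875 = 4.5%
- d = 0, any p: 0

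**3. Simulation of the test itself.** CMH row-mean-scores test with modified ridit scores, rank / (n_h + 1) in stratum h; 7-category outcome; two arms of 120 balanced within smoking strata; two-sided 0.05; 6,000 runs per cell. The placebo category distribution and a latent treatment effect of 0.38 SD (chosen to give about 80% power) are assumptions. The range of d is wider than in step 2 in order to test the conclusion.

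| Smokers | d (SD) | Power, unstratified | Power, stratified | Type I error, unstratified |
|---|---|---|---|---|
| 10% | 0 | 79.5% | 79.3% | 5.5% |
| 10% | 0.2 | 79.2% | 79.2% | 5.4% |
| 10% | 0.5 | 79.2% | 79.7% | 4.6% |
| 10% | 0.8 | 77.7% | 79.3% | 4.8% |
| 20% | 0 | 80.2% | 80.0% | 5.0% |
| 20% | 0.2 | 79.8% | 80.1% | 5.1% |
| 20% | 0.5 | 79.2% | 80.2% | 4.3% |
| 20% | 0.8 | 76.8% | 79.7% | 3.7% |
| 30% | 0 | 79.4% | 79.3% | 5.0% |
| 30% | 0.2 | 78.9% | 79.0% | 4.9% |
| 30% | 0.5 | 78.8% | 80.4% | 4.7% |
| 30% | 0.8 | 75.7% | 80.0% | 4.1% |

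The Monte Carlo standard error of the type I error is about √(0.05 × 0.95 / 6000) = 0.3 points. The gain is nil without a smoking effect, at most about 0.3 points at 0.2 SD, 0.5 to 1.6 points at 0.5 SD, and 1.6 to 4.3 points at 0.8 SD. As d grows the unstratified test becomes conservative; it does not become inflated. Where smoking has no effect, stratifying costs essentially nothing.

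**4. Endpoints already adjusted for baseline.** PGI-S SD has 4 levels and each EQ-5D domain has 5 (12-week SAP 5.3.4 and 5.3.8). If baseline adjustment is done by stratification, crossing with smoking gives 2 × 4 = 8 or 2 × 5 = 10 strata. At 10% smokers, 0.10 × 120 = 12 smokers per arm would be spread over 4 or 5 baseline levels: on average 12/4 = 3 or 12/5 = 2.4 per arm per level. A stratum that contains only one arm contributes nothing to the test.

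**The case against.** **Silence is not a statement.** CMH with modified ridit scores is the usual form of a stratified rank test, so smoking may have been intended and left unnamed. The word *also* in the sentence on PGI-S and EQ-5D could hint at an unstated adjustment. This stands in part: the firm finding is that the stratum is not named. The same plan does name an adjustment for a CMH test where it wants one (baseline score), so unstratified is the natural reading for PGI-C.

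**A reader might infer that real precision is being discarded.** The documents do not support that. They give no smoker share and no effect of smoking on PGI-C. Protocol 1.3.2 reports lower fezolinetant exposure in smokers, which can act only in the active arms. It does not establish the difference across all arms that the variance formula needs.

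**A reader might infer that the meaningful-change threshold is at risk**, because PGI-C VMS was moved to secondary for its potential use as an anchor (protocol Attachment 1). It is not. The thresholds come from a separate psychometric plan, and the responder comparison built on them already includes smoking (12-week SAP 6.4.4).

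**Smoking is not in every analysis.** The simplified MMRM (6.4.1.2) omits it. That is true, but it is a declared sensitivity model. The PGI-C test is the planned analysis of its endpoint.

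**Conclusion.** The point holds as a free improvement of the lowest severity. The two PGI-C tests name no stratum although the trial stratifies by smoking, and read as written they are unstratified.

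The cost is at worst slight conservatism and a small loss of precision: nil if smoking is not prognostic, and about 0.6% to 4.5% of the variance for 10% to 25% smokers and differences of 0.25 to 0.5 SD. In the simulation, a 0.5 SD difference with 10% to 30% smokers corresponds to about 0.5 to 1.6 power points. All of these inputs are assumptions.

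No confirmatory conclusion and no sample size changes. Alpha passes from the co-primaries to PROMIS SD only (12-week SAP 5.2.1 and 6.4.2), so PGI-C VMS is outside that sequence, and PGI-C SD is exploratory. Nor should the point be stretched to all the CMH tests: PGI-S SD and EQ-5D already condition on baseline score.

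**What to change.** In 12-week SAP 6.4.3 (PGI-C VMS) and 6.4.4 (PGI-C SD), state: *CMH row-mean-scores test with modified ridit scores, stratified by randomized smoking status (current vs former/never)*. If an unstratified test is really intended, say so and give the reason.

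For PGI-S SD and EQ-5D, keep the planned baseline-score adjustment. Wording that named smoking alone would drop it. Add smoking there only together with a prespecified rule for pooling sparse strata.

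The cost for the two PGI-C tests is one phrase in the SAP and one variable in the program, with no loss where smoking turns out not to matter. For PGI-S SD and EQ-5D the pooling rule is extra work, so adding smoking there is optional.
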